All participants, regardless of study arm assignment, will be asked to complete the UC Protocol (Appendix H) which consist of a daily regimen of stretching and cryotherapy that includes 3-5 minutes of stretching upon waking, then approximately 3-5 minutes of stretching and 3-5 minutes of cryotherapy throughout the day, for the duration of 6 weeks (instructions and participant handout will be provided, Appendix I).

Participants will receive PBMT or sham-PBMT with the PBM device (Appendix J, Figure 1) over the course of three consecutive weeks (three treatments per week). PBM treatments will take

approximately 5-10 minutes to administer at each session. Specific treatment parameters will be based on measurements of calf, ankle, and foot using pre-calculated treatment tables; participants will receive 10 J/cm2, 25W output power, and the length of the treatment will be dependent on treatment area (size).

Photobiomodulation Therapy (PBMT):

PBMT will be administered by a trained member of the study team using the LightForce® XPi therapy laser, provided by LiteCure, LLC/DJO Global (New Castle, DE). The LightForce® XPi therapy laser is an FDA cleared device for the treatment of pain. The trained team members will use the Smart Hand Piece technology, which achieves effective treatments and improves dosing accuracy by assessing the operator's speed and providing real-time visual (red – amber – green light) and sensory feedback (Appendix J, Figure 2). The Smart Hand Piece is calibrated to shutoff when moving too slowly, and warn the operator when moving too fast by vibrating. The therapy is delivered through a flexible optical fiber threaded through the hand piece, which contains a rolling sapphire massage ball. The PBM therapy will be administered by rolling the massage ball over the plantar surface of the foot and dorsal aspect of the calf in contact with the participants' skin.

Sham-Photobiomodulation Therapy (Sham-PBMT):

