Plantar fascia thickness will be measured by an MSK US trained provider utilizing an ultrasound system. The participant will be identified on the ultrasound system using only the assigned participant ID. The patient will be positioned prone on an examination table with the leg extending off the end so the foot projects downward in a relaxed state. Using a linear transducer for best resolution, the plantar fascia will be evaluated in the long axis to determine the site to be measured as identified by the bony contour demonstrated in Appendix J, Figure 3. The vertical thickness of the plantar fascia will be documented in both long and short axis at this point. The points measured will be from the edge of the bone to the outer layer of the plantar fascia.

Plantar fascia thickness will be measured in two orthogonal planes (90 degrees different - long axis and short axis of the structure) at the site identified by the bone contour in Appendix J, Figure 3. The measurement will be conducted by MSK US trained providers, either in Physical Therapy or Physical Medicine and Rehab clinics.

These images will be uploaded to the Teleray data platform. More information in Managing Data Sections 10.14-10.15.

Missed Appointments and Study Removal:

If a participant misses a scheduled appointment, they will be contacted to reschedule in order to maintain the treatment plan of their assigned study treatment group, (i.e., three times a week, for three weeks). In the event that a participant misses an appointment, study staff will make one attempt to reschedule each day on three separate days (for three total attempts to reschedule). If the participant cannot be reached or does not respond/reschedule, they will be removed from the study due to non-compliance.

A participant adherence log can be found in Appendix N.

A study process flowsheet can be found in Appendix O.

Data Entry:

With the exception of the Intake CRF which collects participant contact information, all coded research data will be entered into REDCap, an encrypted, access controlled, password protected electronic data capture and management system housed on a DoD server and maintained by the Uniformed Services University (USU). No PHI/PII will be entered into REDCap.

See Appendix R for additional information on REDCap.

Additional Info - MIRROR/USU:

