11.5 Please provide a justification for your sample size			
We found that enrolling 78 and retaining at least 60 patients by the six-week follow-up would be sufficient to yield >80% power for a moderate effect size (Mean six-week decrease in FAAM sports subscale: delta = 0.20) and a moderate standard deviation in effect (Std dev of six-week change in FAAM sports subscale: SD = 0.2), assuming the control effect mean and standard deviation are 0 and 0.22, respectively. Under similar constraints but with a standard deviation <0.18, the study would yield power >90%. Power was estimated using 1 million iterations of a Monte Carlo simulation based on effect means and standard deviations estimated from pilot data. Technical details will be made available upon request.			

In order to meet enrollment goals during the expected period of performance, recruitment will be expanded in addition to the current load of plantar fasciitis patients receiving care in the MAMC Orthopaedic and Podiatry clinics (a conservative estimate of approximately 80 patients per month), to reach potential participants receiving care in other departments including Family Medicine, Physical Therapy, and Physical Medicine & Rehabilitation (PM&R) clinics.	
11.6 Data Analysis Plan: Complete description: Background, Objectives, Design, Step by St project is going to be done, Data analysis plan:	ep how the
Descriptive statistics for each variable will be reported as central tendencies in terms of location (e.g., mean, median) and scale (e.g., variance, interquartile interval). Inferential analyses will use the Mann-Whitney U test (a non-parametric analogue of Student's t-test) for simple comparisons and regression analysis with outcome-appropriate distribution families and link functions for multivariable comparisons. The FAAM sports subscale will be standardized by the multiplicative inverse of the patient-level maximum possible score. The primary outcome will be computed as the patient-level, six-week change in standardized FAAM sports subscale. Sensitivity analyses will be conducted using regression to control for patient-level demographics. Hypothesis tests will be two-tailed and statistical significance will be considered at the putative threshold (alpha=0.05). Effect sizes will be compared to a minimum clinically important difference. Data will be analyzed on a complete-case basis with regards to each planned analysis. For	

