example: if a patient has missing data after the 3-month follow-up due to being removed from the study (and they have full data prior to the 3-month follow-up), their data may still be considered for analyses which only consider baseline and the 6-week follow-up but will be omitted from any analyses which consider one or more time points beyond the 3-month follow-up.	
12.0	
Participant Information	
Participant Information 12.1 Subject Population:	
12.1 Subject Population:	
12.1 Subject Population: DEERS eligible, adults between the ages of 18-64 (inclusive) diagnosed with plantar fasciitis (PF).	
12.1 Subject Population: DEERS eligible, adults between the ages of 18-64 (inclusive) diagnosed with plantar fasciitis (PF). 12.2 Age Range: Check all the boxes that apply. if the age range of potential subjects (specimens, records) does not match the range(s) selected, please specify in the text box. □ 0-17 ☑ 18-24 ☑ 25-34 ☑ 35-44 ☑ 45-54 ☑ 55-64 □ 65-74	

Other

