Following completion of informed consent, the results of the Inclusion/Exclusion CRF will be entered into REDCap, an encrypted, access controlled, password protected electronic data capture and management system housed on a DoD server and maintained by the Uniformed Services University Information Technology (USU IT), and a unique study ID will be generated. This coded study ID will be used on all research data collection forms in place of the participant's name, Department of Defense (DoD) ID, or other protected identifier. No PII will be entered into REDCap. Please see Appendix R for additional information on REDCap.

13.5	DoDI 3216.02 requires an ombudsman to be present during recruitment briefings when research
	involves greater than minimal risk and recruitment of Service members occurs in a group setting. If
	applicable, you may nominate an individual to serve as the ombudsman.

N/A

Propose ombudsman

13.6 Withdrawal from Study Participation:

Explain the process for withdrawal and specify whether or not the subjects will be given the opportunity to withdraw their data their data/specimens in the event they wish to withdraw from the study

Participant Withdrawal:

Participants may withdraw from the study at any time without penalty. Participants will be informed that withdrawal will not affect their access to health care that they are otherwise entitled to and it will not affect their military position.

If a participant withdraws from the study, we may retain and analyze all coded/de-identified data collected up to the time of withdrawal if the data is necessary to maintain the integrity of the study. However, no further data will be collected after the date of withdrawal.

Participants may contact the study research coordinator/assistant or Principal Investigator to formally withdraw from the study. Participants will be advised to follow-up with their personal physician if they choose to withdraw.

Withdrawal Without Participant Consent:

A participant may be withdrawn from the study without their consent if remaining in the study might be dangerous or harmful to them. Participation may also be stopped if the military mission requires it, if they lose their right to receive medical care at a military hospital, if the study is canceled, if they fail to adhere to the protocol and/or therapy plan, or if they display inappropriate behavior towards study personnel.

The reason for any withdrawal/removal will be documented.

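### Removing participants for missed appointments, with no later outcome collection described and a complete-case analysis, lets attendance after randomisation restrict the six-week comparison; the likely bias is small and the remedy cheap.

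*Combined protocol and SAP*

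**What the plan says.** **Removal.** Under Missed Appointments and Study Removal, section 10.1 provides one rescheduling attempt on each of three days, and then: "If the participant cannot be reached or does not respond/reschedule, they will be removed from the study due to non-compliance". The participant leaves the study, not only the treatment sessions. Section 13.6 also permits, without requiring, removal of participants "if they fail to adhere to the protocol and/or therapy plan".

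**Timing.** Treatment is given "over the course of three consecutive weeks (three treatments per week"). The primary outcome in section 11.6 is the six-week change in the standardised FAAM Sports subscale.

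**Collection afterwards.** Section 13.6 says that collection stops at the date of withdrawal, but it says this for participants who withdraw themselves. For removal by staff the text is silent.

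**Analysis.** Section 11.6: "Data will be analyzed on a complete-case basis with regards to each planned analysis". The only sensitivity analysis is this: "Sensitivity analyses will be conducted using regression to control for patient-level demographics". An example there treats removal as a cause of missing data ("if a patient has missing data after the 3-month follow-up due to being removed from the study"), although it concerns the 3-month visit.

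**Records kept.** "The reason for any withdrawal/removal will be documented" (13.6), and "A participant adherence log can be found in Appendix N" (10.1). No planned analysis uses either record to examine the effect of loss.

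**The concern.** Randomisation makes the arms comparable for everyone allocated. A complete-case comparison keeps that protection only if loss is unrelated to outcome, or is related in the same way in both arms. Attendance at three sessions a week can depend on how the foot is doing: people who feel no benefit may stop coming, and so may people who have recovered. If that pattern differs between arms, the six-week difference is shifted.

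The trial exists to give a rigorous sham comparison, and section 11.6 will set its effect against a minimum clinically important difference, so a shift of a few hundredths would matter to the interpretation. The adjustment for demographics does not address it. Six-week scores that were never requested cannot be recovered at the analysis stage.

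**Working it through.** **1. The plan's own figures.** Inputs from section 11.5: difference 0.20, SD 0.20 (PBMT) and 0.22 (control), 78 enrolled, 60 retained. Two-sided alpha is 0.05 (11.6).

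- Pooled SD = √((0.20² + 0.22²)/2) = 0.210.
- With 30 per arm, 0.20 / (0.210 × √(2/30)) = 3.68, and 3.68 − 1.96 = 1.72, so power is 95.8%. A Mann-Whitney simulation gives 93.9%. The stated bound of more than 80% is met.
- Section 11.2: 80 / (1 − 0.20) = 100 reproduces the enrolment cap. Section 11.5 implies a loss of 18/78 = 23.1%.

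The point is therefore about bias, not lost power.

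**2. Size of the bias.** The documents do not say how much loss the rule would cause or how it relates to outcome. These are assumptions:

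- 50 randomised and 10 lost per arm;
- a share p of the arm is lost in a way that correlates r with six-week change (lowest values leave), and all other loss is random.

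The completers' mean in that arm then shifts by about r × SD × φ(z_p)/(1 − p), where z_p is the normal quantile at p. The last factor is 0.0862/0.96 = 0.090 at p = 4%, 0.1755/0.90 = 0.195 at 10%, and 0.2800/0.80 = 0.350 at 20%.

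Examples:
- sham arm only, r = 0.5, p = 20%: 0.5 × 0.22 × 0.350 = 0.0385;
- sham arm only, r = 0.5, p = 10%: 0.5 × 0.22 × 0.195 = 0.021;
- both arms, r = 0.5, p = 20%: 0.5 × 0.350 × (0.20 − 0.22) = −0.0035.

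Simulation with no true effect (40,000 runs, 40 analysed per arm, two-sided Mann-Whitney). Each cell gives bias as PBMT minus sham, then rejection rate. Rates are good to about half a percentage point.

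| Outcome-related loss | Sham only, r=0.3 | Sham only, r=0.5 | PBMT only, r=0.3 | PBMT only, r=0.5 | Both, r=0.5 |
|---|---|---|---|---|---|
| 2 of 50 (4%) | −0.006, 5.0% | −0.009, 5.3% | +0.005, 5.0% | +0.009, 5.4% | −0.001, 5.1% |
| 5 of 50 (10%) | −0.012, 5.7% | −0.021, 7.4% | +0.012, 5.5% | +0.019, 6.5% | −0.002, 5.4% |
| 10 of 50 (20%) | −0.023, 7.7% | −0.038, 12.4% | +0.021, 7.1% | +0.034, 11.1% | −0.003, 5.8% |

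If the better responders leave instead, the signs reverse. In the limiting case, where the worst 20% of one arm leave, the bias is −0.075 (sham) or +0.069 (PBMT), and rejection would be above the table's 12%. The FAAM Sports MCID is 9 points (10.2), or 0.09 on this scale, and every bias is below it. At a true effect of 0.20 with sham-only r = 0.5, power is 97.5%, 96.1% and 92.5% down the three rows. It is 83.8% in the sham limiting case.

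**3. What collection after removal would recover.** Take sham only, r = 0.5, 20% lost. Completers average +0.0385 against the arm mean, so the lost average −0.0385 × 0.8/0.2 = −0.154. If a random half of the 10 lost supply a six-week score, the observed mean is (40 × 0.0385 − 5 × 0.154)/45 = 0.017. The bias falls from 0.038 to 0.017 with the primary test unchanged.

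**4. What a model would add.** In the same scenario, suppose early FAAM changes correlate 0.6 or 0.8 with six-week change.

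- Leaving depends on early change: residual bias is 0.000 if everyone has an early value, but about −0.017 if only half of the lost do.
- Leaving depends on the six-week outcome: −0.025 or −0.014 with early values for everyone; −0.031 or −0.025 with half.
- No early values for the lost: no gain (−0.037 to −0.039).

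**The case against.** **The loss may be small and balanced.** The Background reports that all pilot participants adhered to the same nine-session course. Section 10.1 gives both arms the same schedule, a warmed sham and a replicated beep, with unblinding only after six weeks. Section 13.6 lists other causes of loss, such as military mission. This largely stands and is why the bias is called small. It does not settle the matter: pilot controls had no sessions, so the pilot says nothing about attendance at sham sessions, and the plan still allows for about 20% attrition.

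**The higher figures stack assumptions.** They do. The 12% needs all of the assumed loss to be outcome-related in one arm and unrelated in the other. With r = 0.5 in the sham arm and 0.4 in the PBMT arm, the bias is 0.006 (5.2% rejection) at the 10% share and 0.010 (6.0%) at the 20% share.

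**People removed under this rule are those who did not respond.** This is true of some. The rule also covers people who were reached but did not reschedule, and some of them may answer a questionnaire link.

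**Stronger readings to avoid.** A reader might infer that the protocol forbids data collection after removal; the sentence in 13.6 is stated only for participant-initiated withdrawal. A reader might also infer that none is planned. The appendices, including the adherence log and flowsheet, are not in the text reviewed, so one can say only that none is described. Nor does the 11.6 example show six-week loss: it says such participants may stay in the baseline-to-six-week analysis. Finally, the point does not require replacing the primary test. A mixed model or imputation would test a mean difference under its own assumptions rather than ranks, which is a separate choice.

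**Conclusion.** The concern holds in a limited form. As written, some randomised participants can leave the primary comparison because of later attendance, and no planned analysis shows how far the result depends on that.

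The likely effect is small: a bias of about 0.003 to 0.004 or less with similar selection in both arms. It reaches about 0.02 to 0.04, with false rejection up to about 12%, only if half to all of an assumed 20% loss is outcome-related in one arm alone at r = 0.5. These are illustrations; the true share, strength and direction are unknown. The documents do not support calling this a fatal bias, or attributing the whole 20% attrition to the rule. It ranks between minor and should-fix, and is worth correcting because the remedy is cheap and uncollected scores cannot be recovered.

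**What to change.** 1. **Sections 10.1 and 13.6.** Leave the session rule unchanged. State that removal for missed sessions does not end outcome collection unless the participant withdraws consent. Request the 3-week and 6-week FAAM and DVPRS through the REDCap link (10.14) or by phone, which 10.1 now describes only for the 3-month follow-up. Reconcile this with the 13.6 sentence on stopping collection at withdrawal and, if needed, with the consent wording. If an appendix already covers this, say so in both sections.
2. **Section 11.6, primary analysis.** Analyse every randomised participant who has a six-week score in the assigned arm, including those removed from sessions. Keep the planned Mann-Whitney test as primary.
3. **Section 11.6, sensitivity analysis.** Prespecify one missing-data analysis that includes all randomised participants: multiple imputation or a mixed model using baseline and available post-baseline FAAM Sports values, with a delta-adjusted tipping-point step. Report loss and reasons by arm. State which daily FAAM Sports values will exist, because 10.2 lists the FAAM daily on days 2 to 43 but its diary description names only the DVPRS.

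**Cost.** Protocol and SAP wording, possibly consent wording, a few extra contacts and more analysis work; no new participants or instruments. Some removed participants will still not respond. The model gives little or no gain for those without post-baseline values, and it rests on a missing-at-random assumption that the data cannot test. The tipping-point step only shows how much the result depends on it.

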11.5 Please provide a justification for your sample size			
We found that enrolling 78 and retaining at least 60 patients by the six-week follow-up would be sufficient to yield >80% power for a moderate effect size (Mean six-week decrease in FAAM sports subscale: delta = 0.20) and a moderate standard deviation in effect (Std dev of six-week change in FAAM sports subscale: SD = 0.2), assuming the control effect mean and standard deviation are 0 and 0.22, respectively. Under similar constraints but with a standard deviation <0.18, the study would yield power >90%. Power was estimated using 1 million iterations of a Monte Carlo simulation based on effect means and standard deviations estimated from pilot data. Technical details will be made available upon request.			

In order to meet enrollment goals during the expected period of performance, recruitment will be expanded in addition to the current load of plantar fasciitis patients receiving care in the MAMC Orthopaedic and Podiatry clinics (a conservative estimate of approximately 80 patients per month), to reach potential participants receiving care in other departments including Family Medicine, Physical Therapy, and Physical Medicine & Rehabilitation (PM&R) clinics.	
11.6 Data Analysis Plan: Complete description: Background, Objectives, Design, Step by St project is going to be done, Data analysis plan:	ep how the
Descriptive statistics for each variable will be reported as central tendencies in terms of location (e.g., mean, median) and scale (e.g., variance, interquartile interval). Inferential analyses will use the Mann-Whitney U test (a non-parametric analogue of Student's t-test) for simple comparisons and regression analysis with outcome-appropriate distribution families and link functions for multivariable comparisons. The FAAM sports subscale will be standardized by the multiplicative inverse of the patient-level maximum possible score. The primary outcome will be computed as the patient-level, six-week change in standardized FAAM sports subscale. Sensitivity analyses will be conducted using regression to control for patient-level demographics. Hypothesis tests will be two-tailed and statistical significance will be considered at the putative threshold (alpha=0.05). Effect sizes will be compared to a minimum clinically important difference. Data will be analyzed on a complete-case basis with regards to each planned analysis. For	
example: if a patient has missing data after the 3-month follow-up due to being removed from the study (and they have full data prior to the 3-month follow-up), their data may still be considered for analyses which only consider baseline and the 6-week follow-up but will be omitted from any analyses which consider one or more time points beyond the 3-month follow-up.	
12.0	
Participant Information	
Participant Information 12.1 Subject Population:	
12.1 Subject Population:	
12.1 Subject Population: DEERS eligible, adults between the ages of 18-64 (inclusive) diagnosed with plantar fasciitis (PF).	
12.1 Subject Population: DEERS eligible, adults between the ages of 18-64 (inclusive) diagnosed with plantar fasciitis (PF). 12.2 Age Range: Check all the boxes that apply. if the age range of potential subjects (specimens, records) does not match the range(s) selected, please specify in the text box. □ 0-17 ☑ 18-24 ☑ 25-34 ☑ 35-44 ☑ 45-54 ☑ 55-64 □ 65-74	

Other

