If the potential participant meets eligibility criteria as determined by the Inclusion/Exclusion CRF and expresses interest in participating, an authorized study team member will initiate the formal consent discussion and, if applicable, obtain informed consent.

Pre-screening conversations may also take place over the phone using the Screening Script (Appendix M). Potential participants who meet initial eligibility per the Screening Script and express interest in participating will be asked to come to clinic to complete an Inclusion/Exclusion CRF to confirm final eligibility with an authorized study team member prior to providing informed consent.

Baseline Data Collection (post-consent):

Formal Screening:

All consented participants that are biological females of child-bearing age and capacity will be required to complete a urine hCG pregnancy test, which will be ordered via EMR by a study provider, to confirm eligibility for study participation. MAMC Department of Pathology and Area Laboratory Services (DPALS) will complete urine sample collection and analysis and upload results in the participant's EMR. If the pregnancy test is positive, per the inclusion/exclusion criteria, the participant will be formally withdrawn from the study at this point, and will be encouraged to seek care with their primary care physician. If the pregnancy test is negative, the participant will be eligible to continue with the study procedures. The results of the pregnancy test will be entered into the EMR and in the Inclusion/Exclusion CRF.

Prior to receiving their assigned study treatment, participants will provide their contact information (Appendix B Intake CRF) and complete a series of baseline outcome measures (Appendix C Demographics CRF and Appendix D Baseline Data Collection CRF) and have their plantar fascia thickness measured within the Podiatry clinic. A study team member will also acquire measurements of the participant's calf, ankle, and foot to calculate the appropriate PBMT dose (see Appendix L).

If a participant has plantar fasciitis on both feet, only one foot will be eligible to receive study treatment. The primary study foot will be determined by the baseline FAAM score indicating the foot with the most disability.

Randomization:

Participants will be randomly assigned to a study group (PBMT+UC or Sham PBMT+UC) using a computer-generated randomization model prepared by the study biostatistician.

Study Treatments (PBMT+UC or Sham PBMT+UC):

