Musculoskeletal Injury Rehabilitation Research for Operational Readiness (MIRROR), which is based out of the Department of Physical Medicine & Rehabilitation (PM&R) at the Uniformed Services University (USU), is serving as the Data Coordinating Center for this study and will also be providing remote regulatory support. Staff from MIRROR/USU will not interact with human subjects and will not have access to the paper research records or any identifiable research data to include the Master List, the Informed Consent Documents/HIPAA Authorizations, or any other form of participant PHI/PII.

De-identified research data will be shared with MIRROR/USU and maintained indefinitely for possible use in future research.

There will be appropriate data sharing agreements in place.

10.2 Data Collection:

Describe all the data variables, information to be collected, the source of the data, and how the data will be operationally measured.

Instrument Characteristics

Outcome Measure

Demographics The Demographics CRF (Appendix C) and Baseline Data Collection CRF (Appendix D) will be used to obtain Baseline Data demographic information, Fitzpatrick Skin Phototype, Collection CRF and foot, ankle, and calf measurements for PBMT dosage calculation. The Fitzpatrick Skin Prototype is a rating of susceptibility to skin damage from ultraviolet (UV) radiation. (49)

Demographic Information; measurements for dose calculation

Foot and Ankle Ability Measure (FAAM)

The FAAM is a 29-item self-report instrument that assesses physical function in foot and ankle impairments which included PF cases in development. There are two subscales, Activities of Daily Living (21item) and Sports (8-item). Each item is scored on a 5point Likert scale (4='no difficulty at all' to 0='unable to do'); points are transformed to a percentage (100%=no dysfunction). Test-retest 0.89 & 0.87 for ADL & Sports subscale; internal consistency a=.98, minimum clinically important difference 8 & 9 points for ADL & Sports subscale, respectively. (50) (Appendices D-E).

Aim 1: Primary outcome measure for function; collected at baseline, daily days 2-43 (during and post treatment), 3 months.

Pain Diary Defense and Rating Scale (DVPRS)

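### Baseline FAAM Sports enters the primary comparison only by subtraction, and the promised MCID comparison has no defined between-arm estimate or confidence interval

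*Combined protocol and SAP*

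**What the plan says.** Sections 11.1 and 11.6 carry the same analysis text. The endpoint is fixed: "The primary outcome will be computed as the patient-level, six-week change in standardized FAAM sports subscale". For two-group comparisons, "Inferential analyses will use the Mann-Whitney U test". Regression is mentioned generically for multivariable comparisons, with no variables listed. The one covariate set named is in this sentence: "Sensitivity analyses will be conducted using regression to control for patient-level demographics". Section 10.1 keeps the Demographics form (Appendix C) separate from the Baseline Data Collection form (Appendix D), and section 10.2 places the FAAM in Appendices D and E, so demographics does not naturally include baseline FAAM.

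On clinical importance the plan says "Effect sizes will be compared to a minimum clinically important difference". Section 10.2 supplies the value: "minimum clinically important difference 8 & 9 points for ADL & Sports subscale, respectively". No between-arm estimator is named and no confidence interval is mentioned. The descriptive statistics promised are location and scale for each variable.

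Baseline FAAM is available for everyone ("Primary outcome measure for function; collected at baseline"). It also chooses the foot in bilateral cases: "The primary study foot will be determined by the baseline FAAM score indicating the foot with the most disability". Section 11.4 specifies simple randomization, with no stratification stated.

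**The concern.** A change score uses the baseline fully only when the slope of the six-week score on baseline is exactly 1. At any other slope, part of the six-week variation that baseline could explain stays in the error term. Two features make baseline worth modelling here. Taking the worse foot in bilateral cases invites some regression to the mean, and simple randomization leaves room for chance baseline differences between arms. Neither biases the test under randomization; both bear on precision.

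The second gap does not depend on that slope. To compare an effect with 9 points, the plan needs an effect in FAAM points and a measure of its uncertainty. As written, someone must choose after the data are in among a mean difference, a difference in medians, a Hodges-Lehmann shift, an adjusted difference or a within-arm change. A significant p-value or a bare estimate could then be read as having reached 9 points when the data do not support that.

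**Working it through.** **Inputs from the plan**
- Section 11.5: SD of change 0.20 (active) and 0.22 (control), control mean 0, delta 0.20, 60 retained. Section 11.5 words delta as a decrease, although a higher FAAM is better; it is taken here as a benefit of 0.20.
- Section 11.2: up to 100 enrolled, about 20% attrition, so 100 × 0.80 = 80, or 40 per arm. From 60 retained, 30 per arm.
- Sections 11.1 and 11.6: two-sided alpha 0.05.
- Section 10.2: MCID 9 points on a 0–100 scale, which is 0.09 on the 0–1 analysis scale.

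**Assumed, because the documents do not give them:** the baseline to six-week correlation ρ, and k = six-week SD / baseline SD. The reliability figure in section 10.2 ("Test-retest 0.89 & 0.87 for ADL & Sports subscale") gives 0.87 for Sports, taken as an upper limit for ρ. Reading 9 points as a between-group threshold is also an assumption.

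**Step 1: the plan's power.** Root-mean-square SD = √((0.20² + 0.22²)/2) = 0.210. At 30 per arm and 0.20, power is 95.8% (normal formula) and 94.0% (simulated Mann-Whitney). The stated figure of more than 80% holds with room to spare. At 40 per arm, Mann-Whitney gives 98%.

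**Step 2: width against the MCID.** SE = 0.210 × √(2/n), which is 0.0543 (n = 30) and 0.0470 (n = 40). The t-based 95% half-widths are 0.109 and 0.094 (0.108 and 0.093 in simulation). For the lower limit to reach 0.09, the observed difference must be 0.09 + 0.109 = 0.199, or 0.09 + 0.094 = 0.184. In simulation at a true 0.20, the unadjusted interval reaches below 0.09 in about 45% (n = 30) and 35% (n = 40) of trials significant by Mann-Whitney.

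**Step 3: what adjustment buys.**
- Slope = ρk.
- Variance cut = 1 − k²(1 − ρ²)/(1 + k² − 2ρk), which is zero when the slope is 1.
- Example, k = 1, ρ = 0.5: 1 − 0.75/1 = 25%.
- Baseline SD s₀ = 0.21/√(1 + k² − 2ρk).
- Shift in the change-score difference from a one-SE chance baseline imbalance at 40 per arm = (1 − ρk) × s₀ × √(2/40). For k = 1, ρ = 0.5: 0.5 × 0.21 × 0.2236 = 0.023.

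An imbalance of at least one SE occurs in 32% of trials. The shift is the same precision loss as seen in a single trial, not an additional one.

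The variance cut and shift below are closed-form. The last two columns are simulated (normal data, 16,000 runs per cell) with HC3 robust errors, 40 per arm.

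| k | ρ | Variance cut | One-SE shift | Adjusted power at 0.09 | P(lower limit ≥ 0.09) at 0.20 |
|---|---|---|---|---|---|
| 1 | 0.3 | 35% | 0.028 | 63% | 0.80 |
| 1 | 0.5 | 25% | 0.023 | 57% | 0.75 |
| 1 | 0.7 | 15% | 0.018 | 52% | 0.69 |
| 1 | 0.87 | 6.5% | 0.012 | 47% | 0.65 |
| 1.25 | 0.5 | 11% | 0.015 | 49% | 0.67 |
| 1.25 | 0.7 | 2% | 0.007 | 46% | 0.62 |
| 1.25 | 0.8 | 0% | 0 | 45% | 0.62 |
| 0.8 | 0.5 | 43% | 0.031 | 68% | 0.85 |
| 0.8 | 0.7 | 37% | 0.029 | 64% | 0.81 |
| 0.8 | 0.8 | 36% | 0.028 | 64% | 0.81 |

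Unadjusted comparators at 40 per arm: power at 0.09 is 44–45% (Mann-Whitney) and 47–48% (Welch t on change); P(lower limit ≥ 0.09) at 0.20 is 0.63–0.65. Half-width is 0.093 unadjusted, against 0.077–0.093 (k = 1), 0.090–0.096 (k = 1.25) and 0.072–0.077 (k = 0.8) adjusted. HC3 type I error was 4.1–5.1%.

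**Step 4: bounded scores.** Eight 0–4 items, baseline mean 0.50–0.75, ρ 0.25–0.75, 40 per arm. Power at 0.09 is 40–47% (Mann-Whitney) and 45–71% (adjusted). Half-width at 0.20 is 0.089–0.099 unadjusted and 0.061–0.091 adjusted. Adjusted type I error is 4.1–5.1%. These runs assume equal baseline and sham six-week spread, so they do not cover k = 1.25.

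**The case against.** The best defence is that nothing here invalidates the trial. Baseline is already subtracted, the comparison is unbiased under randomization, and power at 0.20 is ample. The generic regression sentence would permit a baseline covariate, and such a model would produce an arm coefficient with an interval. All of that is true. But permitting is not specifying, and the MCID comparison still lacks a named estimate.

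On size, three points stand:
- Part of the gain over Mann-Whitney comes from moving to a mean-based analysis. Against Welch t (47–48% at 0.09), adjustment gains nothing at ρ = 0.87 with equal variances, and loses about 1–3 points at k = 1.25 with ρ of 0.7–0.8. Mann-Whitney remains the relevant comparator, because it is the plan's own test.
- Robust errors use up small theoretical gains. The 6.5% cut at ρ = 0.87 leaves the half-width at 0.093.
- Holding the change SD at 0.21 forces a baseline SD of 0.41 at k = 1, ρ = 0.87, and 0.35 at k = 0.8, ρ = 0.8. These are large on a 0–1 scale, where the maximum is 0.5, so those cells are less credible.

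It is also fair that a difference with a CI would by itself repair the MCID comparison without changing the primary test, and that the documents do not say whether 9 points is a between-group threshold.

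**Conclusion.** The concern holds, as a matter of precision and interpretation rather than validity. Baseline FAAM Sports is used only by subtraction, and the MCID comparison cannot be carried out as written without a choice made later.

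The missing estimate and interval matter whatever ρ is: the half-width (0.109 at 30 per arm, 0.094 at 40) is at or above the 0.09 MCID, so significance alone says little about reaching 9 points. The 45% and 35% figures rest on the plan's SDs, a true difference of 0.20 and the between-group reading of 9 points. The benefit of adjustment is likely but not guaranteed: a variance cut from 0 to 43% over the range examined, and at a true 0.09 with 40 per arm, power of 45–68% against about 45% for Mann-Whitney. At 0.20 it changes little. The plan should be amended.

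**What to change.** In sections 11.1 and 11.6:

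1. Make the primary analysis a linear model of six-week standardized FAAM Sports on arm and baseline FAAM Sports, with HC3 robust standard errors.
2. Report the adjusted mean difference with its 95% CI in FAAM points beside the 9-point value in section 10.2, and state whether that value is being read as a between-group threshold.
3. Keep Mann-Whitney on the change score, with the Hodges-Lehmann estimate, as a sensitivity analysis.
4. Add baseline FAAM Sports to the demographic-adjusted regression.
5. Adjust DVPRS and fascia thickness for their own baselines in the same way, without an MCID comparison, since the documents give none for them.

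If the team prefers to keep Mann-Whitney as primary, item 2 with an unadjusted mean difference and CI is the minimum repair.

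The cost is SAP wording, with no extra data. Section 10.1 has sham participants unblinded at six weeks, so the change should be dated and locked before anyone sees outcomes by arm. The statistical downside arises when the slope is near 1: at ρ = 0.8 and k = 1.25 the gain is nil and the interval is about 3% wider (0.096 against 0.093 with 40 per arm), with power at 0.09 equal to Mann-Whitney (45%) and slightly below Welch t.
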